We propose a randomized controlled trial to investigate maternal and fetal free radical activity in laboring patients with Category II EFM exposed to O₂ or RA. A randomized controlled trial, the ‘gold-standard’ of study design, was chosen to produce high quality evidence on the safety of O₂ administration for Category II EFM. Our central hypothesis is that prolonged intrauterine exposure to O₂ during labor, compared with RA, generates free radicals that have downstream biochemical and clinical consequences to the neonate. This trial will be conducted on Labor and Delivery (L&D) at Washington University Medical Center (WUMC). Patients ≥37 weeks gestational age in active labor (≥6 centimeters cervical dilation) with Category II EFM necessitating intrauterine resuscitation (as determined by the care provider team) will be randomized to RA or maternal O₂ administration of 10L/min via nonrebreather face mask until delivery. All other resuscitation techniques (maternal repositioning, intravenous fluid bolus, etc) will be left to the discretion of the care provider team. EFM strips will be read and interpreted by the study nurse coordinator. Maternal blood, collected at randomization and within 1 hour post-delivery, placenta and umbilical artery blood collected at the time of delivery will be used to run MDA analyses. Maternal urine will be collection on enrollment (prior to rupture of membranes or cervical dilation <6cm), at time of randomization, and within 1 hour of delivery. At any of these time points, if patient has a foley catheter, the urine may be collected from the catheter. If patient does not have a catheter, either a straight catheterization can be performed or a clean catch sample can be obtained. The same commercially available assays used to quantify MDA and 4-HNE in our blood samples will be used for the urine samples.

Study staff will extract data from medical records including maternal demographics, antepartum history, intrapartum management, delivery outcomes, and neonatal outcomes. The patient’s primary nurse will perform real-time documentation of O₂ or RA initiation, any disruption in intervention, administration of amnioinfusion and additional resuscitation techniques performed (number of times patient is repositioned, total intravenous fluids, discontinuation of oxytocin).

Conduct of Trial

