Study site and population: There are approximately 4000 deliveries per year at Barnes Jewish Hospital (BJH). BJH is an academic, tertiary care center. As a large urban referral hospital, there is a diverse patient population composed of 55% Caucasian, 30% African American, and 15% other racial groups. Patients are largely managed by resident physicians under the supervision of faculty of the Washington School of Medicine (WUSM) and non-academic community OB/GYN physicians.

Inclusion and Exclusion criteria: Patient meeting the eligibility criteria in Table 1 will be approached for enrollment in the trial:

[figure not shown]
Table 1: Inclusion and Exclusion Criteria

| Inclusion Criteria | Exclusion Criteria (Rationale) |
|--------------------|--------------------------------|
|--------------------|--------------------------------|

| | |
|--|--|
| 
 • Singleton term pregnancy: gestational age ≥ 37 weeks • Admitted for spontaneous labor or induction of labor • English speaking • Ability to give informed consent • COVID-19 Negative Result within the last 5 days, previously COVID-19 positive, but meet CDC criteria considered to be “non-infectious”, have a pending COVID-19 test with no symptoms of COVID-19, and/or has been vaccinated for COVID-19 and no recent COVID-19 exposures. | 
 • Major fetal anomaly (increased a priori risk for neonatal morbidity) • Multiple gestation (unique considerations for labor management) • Category III EFM (need for expedited delivery) • Maternal hypoxia (Absolute indication for O2 administration) • Umbilical artery Doppler abnormalities (placental insufficiency that impacts O2 transfer to fetus) • Preeclampsia (increased a priori risk for oxidative stress) • Intrauterine growth restriction (increased a priori risk for oxidative stress) • Pregestational diabetes (increased a priori risk for oxidative stress) • Current tobacco smoker • COVID-19 Positive and do not meet CDC criteria for “non-infectious” • Declined COVID-19 Testing |
|--|--|

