Recruitment of Subjects and Randomization: We will use established recruitment techniques employed in recent RCTs performed on L&D at BJH. All women admitted to L&D in spontaneous labor or induction of labor will be screened with the above inclusion and exclusion criteria. Eligible subjects will be approached for written consent to participate on admission to L&D, irrespective of starting cervical dilation. Randomization will be performed only when the patient is in active labor (defined as cervical dilation ≥ 6 cm) and develops Category II EFM necessitating intrauterine resuscitation as determined by the care provider team (**Figure 3**). Using a computer-generated sequence in block sizes of 4, patients will be randomized in a 1:1 ratio to either O₂ or RA.

Figure 3: Enrollment and Randomization of Study Participants

Intervention

1. **O₂ group:** Patients in this group will receive O₂ via nonrebreather face mask at 10L/min (FiO₂ approximately 0.80) [55]
2. **RA group:** Patients in this group will be exposed to RA only and not wear an O₂ mask unless required for maternal hypoxia (FiO₂ approximately 0.21).

Primary Aim 1

Determine the effect of RA, compared with O₂, on maternal and fetal free radical activity.

1. **Hypothesis:** RA, compared with O₂, for Category II EFM in labor will result in lower mean maternal and umbilical cord levels of malondialdehyde, a byproduct of free-radical-mediated lipid peroxidation and a marker of oxidative stress.
2. **Rationale:** MDA and 4-HNE are downstream products of free radical buildup from excess O₂ and are known markers of oxidative stress.. The current use of O₂ for Category II EFM may result in prolonged exposure that generates free radicals and resultant oxidative stress.
To explore the feasibility of MDA analysis in laboring patients and to provide preliminary data for sample size calculation, we performed the Thiobarbituric Acid Reactive Substances (TBARS) assay for MDA quantification in a subset of maternal (n=27) and UA (n=33) samples exposed to O₂ in the above mentioned pilot trial. The mean maternal MDA was 6.5 μ M \pm 1.0 and the mean UA MDA was 8.3 μ M \pm 2.0. Although no conclusions regarding oxidative stress can be made from this data alone, these results demonstrate feasibility of MDA analysis in this setting.

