5. Data analysis: The primary analysis will be by intention-to-treat. Baseline demographics and secondary outcomes will be compared between RA and O₂ groups using χ^2 , Fisher exact test, Mann-Whitney *U* test, or Student's *t* test as appropriate. The primary outcome, mean maternal and UA MDA, will be compared between groups using the Student's *t* test if normally distributed. If non-normally distributed, the median maternal and UA MDA levels will be compared between groups using the Mann-Whitney *U* test. Linear regression will be used to adjust for relevant covariates. We will perform supplementary analyses including 1) stratified analysis by presence of maternal comorbidities or fetal growth restriction to assess if the effect of O₂ on oxidative stress varies in patients with fetal growth restriction or comorbidities. (2) as-treated analysis to determine whether compliance with the assigned group affects outcomes.
6. Sample size calculation: Based on pilot trial data, the mean UA MDA in 33 patients receiving O₂ for Category II EFM in active labor is $8.3 \pm 2.0 \mu\text{M}$. Assuming a two-sided alpha of 0.05, a total **212 patients (106 O₂ and 106 RA)** will afford 80% power to detect a 10% difference mean UA MDA between O₂ and RA groups, while accommodating for 15% loss due to UA samples. A 10% difference in UA MDA levels may be meaningful as neonatal MDA differences as small as 3-5% are associated with free-radical mediated injuries such as hypoxic ischemic encephalopathy [28, 57] There is limited published data on maternal MDA levels and associated adverse outcomes. However, this sample size will afford >90% power to also detect a 10% difference in maternal MDA between groups. To accommodate a compliance run-in of 6 patients, a total of **218 patients** will be recruited.

Feasibility of the sample size: BJH delivers approximately 4,000 patients per year. Based on results of our pilot trial, 32% of the approached patients meeting eligibility criteria consented to participation in the study. Of the patients enrolled, 40% met criteria for randomization (Category II EFM necessitating intrauterine resuscitation after 6cm dilation). In total, 114 patients were randomized over the study period of 12 months. Therefore, we anticipate successful enrollment of 212 patients within 2.5 years (70-72 patients/year).

Secondary Aim 1:

Investigate the relationship between duration of RA or O₂ exposure and magnitude of oxidative stress

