Anticipated challenges and safeguards: A potential limitation of the study is the inability to blind patients and healthcare providers to the allocation, however, the assessors will be blinded to allocation to limit bias in data analysis. Allocation concealment via use of opaque sealed envelopes will also limit selection bias. Bias could result from nurses and physicians managing subjects differently based on knowledge of their group assignment. To minimize this, providers will be specifically instructed to apply all other intrauterine resuscitation techniques as needed, irrespective of their group assignment. Any additional intrauterine resuscitation that is performed will be documented. To maximize adherence to protocol, we will conduct nursing and physician education sessions.

Protection of Human Subjects/Approvals

1. Risks to human subjects-

1A. Human subjects' involvement, characteristics, and design- The study will enroll 212 patients to investigate whether intrapartum O₂ administration in patients with Category II EFM is associated with oxidative stress. The study population will be English-speaking. Amongst the patients enrolled in the pilot trial, 77% were African American, 14% were Caucasian, 4% were Hispanic, and 5% were of other ethnicities. [name] and the other study members have completed the training module required by the WUSM Human Research Program Office and received education on the responsible conduct of research. The preceding pilot trial was approved by the IRB at WUSTL (IRB ID 201602164) and registered at ClinicalTrials.gov (ID NCT02741284).

1B. Sources of materials-

The study will involve collection of data from two key components:

- 1) Clinical Data Collection** from the medical records of mother and child. For all subjects, these data will be stored in a secure, password-protected REDCap database anonymized with study identifier only.
- 2) Maternal and cord blood samples**: All blood samples will be stored in a locked freezer that only the research team has access to. The maternal/ cord blood and placenta outcomes assessed in this study are additional materials collected for the purpose of the study and are not a part of routine prenatal care. Maternal and cord blood/placenta malondialdehyde levels are not used clinically and at present, cannot be directly linked to clinical outcomes. This will be disclosed to all study participants.

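### The supplementary as-treated analysis is not a randomized comparison and is confounded if women who cross over differ in underlying MDA; a complier-average effect would be a better supplementary analysis of non-compliance

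*Combined protocol and SAP*

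**What the plan says.** All places are in the combined protocol and SAP.

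- **Primary Aim 1, item 5 (Data analysis).** "The primary analysis will be by intention-to-treat". One of two supplementary analyses is an "as-treated analysis to determine whether compliance with the assigned group affects outcomes". The plan does not define the groups by treatment received, say how mixed exposure is handled, name confounders or mark the result as non-randomized. On adjustment it says only "Linear regression will be used to adjust for relevant covariates"; no covariates are named, and the sentence is not tied to the as-treated analysis.
- **Intervention.** Women in the room-air (RA) arm will "not wear an O₂ mask unless required for maternal hypoxia". This is the only written route from RA to O₂. Table 1 excludes women who are already hypoxic: "Maternal hypoxia (Absolute indication for O2 administration".
- **Anticipated challenges and safeguards.** The plan concedes "the inability to blind patients and healthcare providers to the allocation" and adds: "Bias could result from nurses and physicians managing subjects differently based on knowledge of their group assignment". Staff are told to apply other resuscitation measures regardless of arm, and education sessions are planned to support adherence.
- **Overview.** The primary nurse keeps "real-time documentation of O₂ or RA initiation, any disruption in intervention", and also records repositioning, fluids, amnioinfusion and stopping of oxytocin. Treatment received and co-interventions are therefore available for analysis.

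No crossover rate is stated, and no randomization-based analysis of non-compliance is planned.

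**The concern.** The intention-to-treat comparison is protected by randomization; a comparison by oxygen received is not. A woman assigned to RA who is later given O₂ is moved because something happened to her or because of a decision by unblinded staff. The written reason, maternal hypoxia, concerns her condition. If such women would have had different MDA whatever oxygen they received, the as-treated O₂ group gains them, the as-treated RA group loses them, and part of the difference reflects who crossed over and not what O₂ did.

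At stake is a supplementary result that could show an O₂ effect where none exists, or exaggerate a real one, and could then be cited in support of the primary result. The plan's background gives some reason to expect higher MDA in crossovers: it says reoxygenation after hypoxia may generate free radicals and links raised neonatal MDA to hypoxic-ischaemic encephalopathy.

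**Working it through.** **Inputs from the documents (Primary Aim 1, item 6).** Umbilical artery (UA) MDA mean 8.3 µM, SD 2.0 µM; target difference 10%, i.e. 0.1 × 8.3 = 0.83 µM; two-sided alpha 0.05; 80% power; 15% loss of UA samples; 106 per arm.

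**Reproducing the plan's figure.** n per arm = 2 × (1.96 + 0.842)² × 2.0² / 0.83² = 91.2, rounded up to 92. Then 92 × 1.15 = 105.8, i.e. 106 per arm and 212 in total, as stated. After 15% loss, 106 × 0.85 ≈ 90 per arm are evaluable, with power 79.5%.

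**Assumptions, because the documents give no figures.** A share *c* of RA women receives O₂; no O₂-arm woman goes without; crossovers have underlying UA MDA higher by *g* than non-crossovers; SD is 2.0 within each type of woman. The values *c* = 2–20% and *g* = 1 or 2 µM (0.5 or 1 SD) are illustrative.

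**As-treated bias.** Measure MDA from the non-crossover mean.
- The O₂ arm contains the same share *c* of women of the crossover type, so its *n* women contribute a total excess of *ncg*.
- The *nc* RA women who cross over add another *ncg*.
- The as-treated O₂ group has *n*(1 + *c*) women, so its mean excess is 2*cg*/(1 + *c*). The as-treated RA group has excess 0.

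Bias = 2*cg*/(1 + *c*), whatever the true effect. Example: *c* = 0.10, *g* = 1 gives 0.20/1.10 = 0.18 µM.

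| *c* | Bias, *g* = 1 | Bias, *g* = 2 | Share of 0.83 µM | False-positive rate, *g* = 1 / *g* = 2 |
|---|---|---|---|---|
| 0% | 0 | 0 | 0 | 5% / 5% |
| 2% | 0.04 | 0.08 | 5–9% | about 5–6% |
| 5% | 0.10 | 0.19 | 11–23% | 6.0% / 9.4% |
| 10% | 0.18 | 0.36 | 22–44% | 9.3% / 21.0% |
| 20% | 0.33 | 0.67 | 40–80% | 18.4% / 53.0% |

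The rates at 5–20% come from simulation with no true effect (10,000 runs, 90 per arm, nominal 5% t test). At 2% the shift is only 0.04/0.30 to 0.08/0.30, or 0.13 to 0.26 standard errors, which leaves the rate between 5% and 6%.

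**Two-way crossover.** If a share *c* departs in each arm, with excess *g*₁ in RA women who receive O₂ and *g*₂ in O₂-arm women who do not, the bias is 2*c*(*g*₁ − *g*₂). At 10% it is 0.20 µM for *g*₁ = 1, *g*₂ = 0, and zero for *g*₁ = *g*₂. A negative *g*₁ with *g*₂ = 0 reverses the sign.

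**Complier-average effect.** With one binary instrument and no covariates this is the intention-to-treat difference divided by the difference in uptake, here 1 − *c*. At a true effect of 0.83 and *c* = 10%: intention-to-treat 0.83 × 0.90 = 0.747, and 0.747/0.90 = 0.83. It is centred on the truth (0 or 0.83) in every one-way setting above. Its standard error is 2.0 × √(2/90)/(1 − *c*) = 0.31, 0.33 and 0.37 µM at 5, 10 and 20% crossover, against 0.30 for intention-to-treat; the simulation gave up to 0.40.

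It gains no power, since numerator and standard error are divided by the same quantity. Intention-to-treat power at 90 per arm is 75, 71 and 61% at 5, 10 and 20% crossover.

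**Where the complier estimate fails.** If assignment itself shifts MDA by 0.2 µM through other care, then with no O₂ effect and *c* = 10% it returns 0.2/0.90 = 0.22 µM. If the 20% who cross over receive half the effect but are coded as fully treated, it returns 0.83 × (1 − 0.10)/0.80 = 0.93 µM instead of 0.83.

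**The case against.** The case against has real force.

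- **The written crossover route is narrow.** Only maternal hypoxia is named, hypoxia at entry is an exclusion, and the plan includes adherence training and a compliance run-in. If crossover stays at 1–2%, the bias is negligible. This stands, and it is why the low end belongs in the range. A reader might infer that crossover for fetal condition is also provided for. It is not; it would be a guess from unblinded care.
- **The direction is not established.** A reader might infer that the bias must favour O₂ harm. The documents give no MDA values by maternal oxygenation. The background remark on reoxygenation is partly about an effect of O₂ itself and not only about selection. Interruptions in the O₂ arm could offset the bias. The direction is therefore conditional.
- **The complier effect is not a like-for-like replacement.** It would be too strong to say that it answers the plan's question without bias. The plan asks whether compliance affects outcomes; the complier effect is the effect of O₂ in women whose exposure follows assignment. It requires that assignment act only through O₂ received, which the plan's own warning about differential management puts in some doubt. The instruction to treat both arms alike and the recording of co-interventions limit that doubt but do not remove it.
- **The analysis is supplementary.** No primary estimate, sample size or stopping rule depends on it.

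None of this restores randomization to the as-treated comparison, and the plan does not mark the result as non-randomized.

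**Conclusion.** The point holds in conditional form. The as-treated analysis is open to confounding by the reasons for crossover, and nothing in the plan controls for that. Its size cannot be fixed from the documents. For one-way RA-to-O₂ crossover, with crossovers' MDA 1–2 µM above that of non-crossovers, it runs from trivial at 2% crossover to 40–80% of the design difference at 20%. It vanishes without crossover or without a prognostic difference, and can cancel when departures are symmetric.

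A reader might conclude that the trial's main result is undermined. It is not: the primary analysis is by randomized arm and is untouched by this bias. This is an inexpensive improvement to a supplementary analysis.

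**What to change.** In Primary Aim 1, item 5:

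1. Define O₂ received as yes/no, with a rule for brief or interrupted exposure. A version in minutes would need a linear dose effect, whereas the rationale for the duration aim describes a trend concentrated in the first hour.
2. Report crossover in both directions, with reasons, by randomized arm.
3. Make the supplementary non-compliance analysis a complier-average effect by two-stage least squares, with randomized arm as instrument for O₂ received and the same covariates as the main adjusted model. Those covariates need to be named first.
4. State the assumptions: assignment acts only through O₂ received, and no woman would do the opposite of her assignment in both arms (monotonicity). Tabulate the recorded co-interventions by arm, and show how the estimate moves under a small direct effect of assignment.
5. If an as-treated table is kept, label it descriptive and non-randomized.

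**Cost.** SAP wording and one extra model on data already being recorded. The complier estimate has a somewhat wider confidence interval than intention-to-treat, rests on added assumptions, gains no power, and applies only to women whose exposure follows assignment.

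### The recruitment forecast contradicts itself: 70-72 patients a year for 2.5 years gives 175-180, not 212; separately, the 15% sample-loss allowance is slightly short (about 79% power, not 80%)

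*Combined protocol and SAP*

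**What the plan says.** All the figures are in Primary Aim 1 of the combined protocol and SAP, in item 6 (Sample size calculation) and the paragraph after it (Feasibility of the sample size).

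- **Target.** 212 patients, 106 per arm, which "will afford 80% power to detect a 10% difference mean UA MDA between O₂ and RA groups". The same sentence says that this number already allows for lost cord samples: "while accommodating for 15% loss due to UA samples". Six run-in patients bring the number to be recruited to 218.
- **Pilot rate.** "In total, 114 patients were randomized over the study period of 12 months".
- **Forecast.** From the pilot experience the plan concludes that it expects "successful enrollment of 212 patients within 2.5 years (70-72 patients/year").

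No formula is given for the loss allowance, and no date is set on which recruitment must close.

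**The concern.** The forecast puts a number, a period and an annual rate in one sentence, and the rate times the period falls well short of the number. The pilot rate just before it points to a third duration. The paragraph is the plan's only argument that the sample size can be reached, so a reader cannot tell which period to plan for. The timing of the interim analysis and of the data and safety monitoring board meeting also follows from it, because both are set at 50% recruitment.

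The sample size has a smaller problem of its own. The stated 106 per arm looks like the required number multiplied by 1.15. Allowing for a 15% loss means dividing by 0.85, so the allowance would not quite cover the loss that it names.

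**Working it through.** **Recruitment forecast.** Inputs, all from the feasibility paragraph and item 6: 212 patients, 218 with the run-in, 2.5 years, 70-72 a year, pilot 114 in 12 months.

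- Stated rate × stated period: 70 × 2.5 = 175; 72 × 2.5 = 180. Shortfall against 212: 37 and 32 patients (17% and 15%).
- Time needed for 212 at the stated rate: 212/72 = 2.94 years; 212/70 = 3.03 years.
- Time needed for 218: 218/72 = 3.03 years; 218/70 = 3.11 years.
- Rate needed for the stated period: 212/2.5 = 84.8 a year; 218/2.5 = 87.2 a year.
- At the pilot rate: 212/114 = 1.86 years; over 2.5 years, 114 × 2.5 = 285 patients.
- 212/3 = 70.7, so the quoted rate fits a three-year period.
- Half of 212 is 106. At 70-72 a year that is reached at 106/72 = 1.47 to 106/70 = 1.51 years; at 84.8 a year it is reached at 1.25 years.

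**Sample size.** Inputs from item 6: "Assuming a two-sided alpha of 0.05"; 80% power; UA MDA mean 8.3 µM with ± 2.0 read as a standard deviation, from 33 pilot patients on oxygen; a 10% difference. Allocation is 1:1.

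- Difference: 0.10 × 8.3 = 0.83 µM. Standardized difference: 0.83/2.0 = 0.415.
- Evaluable per arm, normal approximation: 2 × (1.960 + 0.842)² / 0.415² = 91.1, rounded up to 92. The t-test calculation gives 92.1, rounded up to 93.
- Reproducing the plan: 92 × 1.15 = 105.8, rounded up to 106 per arm, total 212. This matches exactly.
- Dividing instead: 92/0.85 = 108.2, rounded up to 109 per arm, total 218 before the run-in (t-based: 93/0.85 = 109.4, rounded up to 110, total 220).
- Evaluable at the stated size: 106 × 0.85 = 90.1 per arm.

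| Evaluable per arm | Power, t-test | Power, normal |
|---|---|---|
| 106 (no loss) | 85.3% | 85.6% |
| 92 | 79.9% | 80.4% |
| 90.1 (15% loss) | 79.1% | 79.5% |

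**The case against.** **The target is a count.** A reader might infer that the trial will close at 2.5 years with 175-180 patients and so miss its power. With 15% loss that would leave 74.4-76.5 evaluable per arm and 71-72% power by t-test. The documents do not support this reading. Item 6 commits to 212 and 218. Secondary Aim 1 (item 4) and section 1A of the human subjects part repeat 212. The interim analysis is triggered by a fraction recruited. The 2.5 years is only an expectation, and a wrong expectation delays completion without changing the sample size. This objection stands in full. It also means there is no calendar stop to remove.

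**The pilot rate makes 212 reachable.** At 114 a year, 2.5 years would yield 285, and planning below the observed rate is ordinary caution. That stands as a defence of feasibility, and it means the pilot rate is no contradiction in itself. It does not repair the sentence, because the plan gives 70-72 a year as its forecast and does not explain the step down from 114. The rate may be left over from a three-year plan, but that is a guess.

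**The loss allowance is inferred and immaterial.** No formula is stated, and the match with 92 × 1.15 holds for the normal approximation only (93 × 1.15 rounds up to 107). The shortfall is under one percentage point. The standard deviation, from 33 patients, is far less certain: assuming normality, its 95% interval is about 1.6-2.6, which moves power at 90 per arm between about 55% and 93%. All of this is fair and keeps the point minor. Whatever formula was used, though, 106 less 15% leaves about 90, below the 92-93 required.

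**Conclusion.** The forecast is wrong as written. This rests on multiplication alone: 70-72 a year yields 175-180 in 2.5 years, and 212 needs 2.9-3.0 years (218 needs 3.0-3.1). It is an inconsistency in the feasibility argument. It changes no analysis and does not reduce power.

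The loss allowance is a separate, minor point. With 15% loss, the stated size gives about 79% power (79.1% by t-test, 79.5% by normal approximation). That assumes ± 2.0 is a standard deviation common to both arms, which the exact reproduction of 212 supports, and that the loss is equal in the two arms. That a factor of 1.15 was used is an inference from the match.

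The 71-72% figure applies only if recruitment were closed at 2.5 years at the stated rate, and nothing in the plan says that it would be.

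**What to change.** 1. In the feasibility paragraph, make the period and the rate agree. Either give about 3 years at 70-72 a year, or keep 2.5 years and give about 85 a year (87 if the forecast is for all 218 recruited), with a sentence justifying that rate from the pilot's 114 in 12 months. Say whether the forecast refers to 212 or 218.
2. In item 6, state power as about 79% after 15% loss of UA samples, and state how the loss was allowed for. Holding 80% instead would take 109 per arm (218 randomized, 224 recruited with the run-in) by the normal approximation. For less than one point of power, restating is enough.

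The cost is a change to two sentences, with no extra patients and no change of design. The timeline and the power become slightly less favourable on paper.

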1. Background, rationale, and hypothesis: Khaw et al demonstrated a dose response relationship between maternal MDA concentration and duration of O₂ exposure in a RCT of patients randomized to 60% O₂ by facemask or RA during scheduled cesareans [10]. In an analysis of 27 maternal MDA samples among patients randomized to O₂ in our pilot trial, we found higher median MDA levels in patients who received O₂ for 30-60 mins compared to those who received O₂ for <30 mins. This trend in maternal MDA, particularly in the first 60 minutes of O₂ exposure, suggests a dose-dependent relationship between

duration of O₂ exposure and maternal oxidative stress (unpublished, [name] et al). Here, we will test the hypothesis that duration of O₂ exposure correlates with levels of maternal MDA and 4-HNE.

2. Data collection: Study staff will draw maternal blood at time of randomization and within 1 hour of delivery. Because patients will be randomized to O₂ or RA when they have Category II EFM at any point after 6cm cervical dilation, durations of exposure will vary within groups. Since it is not feasible to sample the umbilical cord at multiple time points, this analysis will be restricted to maternal MDA and 4-HNE.
3. Outcome and data analysis: The primary outcome is mean maternal MDA and 4-HNE in O₂ exposed patients. We will compare mean MDA and 4-HNE across 5 pre-specified durations of O₂ exposure (<30 mins, 30-45 mins, 45-60 mins, 60-90 mins, or >90 minutes) using the one-way ANOVA test. If results of the ANOVA test suggests unequal means, the Tukey post hoc test will be used to identify the groups that differ. Linear regression will also be used to assess the effect of duration of exposure on MDA and 4-HNE concentrations.
4. Estimated statistical power: Maternal MDA differed significantly between 22 patients exposed to O₂ for <30 mins and 20 patients exposed to O₂ for 30-60 mins (unpublished, [name] et al). Based on these data we estimate that the sample size of 212 (106 in the O₂ group) will provide adequate power to detect differences between at least 2 of the 5 groups.

1. .

Secondary Aim 2: Determine the relationship between maternal serum and urine markers of oxidative stress during labor

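### The planned duration analysis has no arm-by-duration term, so as written it cannot separate time on O₂ from elapsed labour

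*Combined protocol and SAP*

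**What the plan says.** The aim appears as Primary Aim b) in Specific Aims and again as Secondary Aim 1 in the methods. Both headings name duration of RA or O₂ exposure. The analysis in Secondary Aim 1 is narrower:

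- Hypothesis (item 1): "we will test the hypothesis that duration of O₂ exposure correlates with levels of maternal MDA and 4-HNE".
- Outcome (item 3): "The primary outcome is mean maternal MDA and 4-HNE in O₂ exposed patients".
- First test (item 3): "We will compare mean MDA and 4-HNE across 5 pre-specified durations of O₂ exposure", by one-way ANOVA with Tukey comparisons if the means differ.
- Second test (item 3): "Linear regression will also be used to assess the effect of duration of exposure on MDA and 4-HNE concentrations". No population, covariate or interaction is given.
- Power (item 4): described as adequate for the 106 O₂ patients, with no effect size or percentage.
- Sampling (item 2): "Study staff will draw maternal blood at time of randomization and within 1 hour of delivery", in both arms. Item 2 also notes that "durations of exposure will vary within groups".

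The Overview says patients are "randomized to RA or maternal O₂ administration of 10L/min via nonrebreather face mask until delivery". The pilot signal that supports the aim comes from "27 maternal MDA samples among patients randomized to O₂ in our pilot trial". The section on the importance of the knowledge to be gained says that what is learned about duration will guide how O₂ is used.

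**The concern.** Within the O₂ arm, a patient with a long exposure is a patient who took a long time to deliver after randomization. If maternal MDA or 4-HNE changes as labour goes on, the long-exposure bands will differ from the short ones whether or not O₂ accumulates any effect. The RA arm shows what elapsed labour does without O₂, and its blood is drawn at the same two times, but the plan does not say it is used for this aim.

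The case that matters is a real but constant O₂ effect together with a shared labour trend. The randomized comparison would then be correctly positive. The O₂-only duration gradient would look like supporting dose-response evidence, and the protocol intends that evidence to inform practice.

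**Working it through.** **1. Inputs from the documents.** 106 patients per arm. Maternal MDA 6.5 µM, SD 1.0 (pilot, Primary Aim 1 item 2). UA MDA 8.3 µM, SD 2.0. Two-sided alpha 0.05. The plan's yardstick is a 10% difference: 0.83 µM for UA and 0.65 µM for maternal MDA.

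**2. The plan's own figures.** n per arm = 2(1.96 + 0.84)² × 2.0² / 0.83², which rounds up to 92. Then 92 × 1.15 = 105.8, so 106 per arm and 212 in total, as stated. Maternal power for 0.65 µM with SD 1.0 and 106 per arm is 99.7%, consistent with the stated figure above 90%. The duration aim's power has no number to reproduce. With five equal bands (106 / 5 ≈ 21) and SD 1.0, the ANOVA needs a gap of about 1.1 µM between two bands, the others midway, for about 80%.

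**3. What each test estimates.** Let T be time from randomization to delivery, D time on O₂, and A the arm (1 for O₂). Write MDA = a + bA + cT + d(A × D), where c is the labour trend and d the O₂-duration effect. Since O₂ runs to delivery, D ≈ T in the O₂ arm.

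- Five-band ANOVA or O₂-only regression: responds to c + d.
- Pooled regression with arm and T but no interaction: about c + d/2 under 1:1 allocation.
- Arm-by-time term: d alone.

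Recorded interruptions help little. With up to 30% (or 50%) of the time off O₂, D still correlates 0.99 (0.96) with T.

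Direct check of the ANOVA by simulation, with assumed median durations of 45 / 60 / 90 min: a pure labour slope of 0.25 µM/h gives significance in 30 / 38 / 52% of trials. An O₂-specific slope of the same size gives 30 / 37 / 50%. The test cannot tell them apart.

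**4. Illustrative size.** Assumptions not in the documents: lognormal T, median 60 min, log-SD 0.8, same in both arms; randomization and post-delivery MDA correlated 0.5; a labour trend shared by both arms, expressed as the correlation r of MDA with log time. On this distribution the mean log times of the under-30 and over-90 min bands are about 2.56 SD apart, so the rise between them is 2.56 × r × 1.0 µM. The O₂ effect is a constant 0.65 µM, with d = 0.

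| r | Rise, extreme bands (µM) | % of 6.5 | ANOVA and randomized test both positive | Arm-by-log-time rejects |
|---|---|---|---|---|
| 0 | 0 | 0 | about 5% | about 5% |
| 0.1 | 0.26 | 4 | about 10% | about 5% |
| 0.2 | 0.51 | 8 | about 28% | about 5% |
| 0.25 | 0.65 | 10 | about 45% | about 5% |
| 0.3 | 0.77 | 12 | about 62% | about 5% |

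With no O₂ effect at all, both tests are positive in under 4% of trials even at r = 0.3, because the randomized comparison is then null.

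**5. Precision of the interaction.** Per SD of log time, the standard error of the O₂-only slope is about 1/√106 = 0.097 (0.098 simulated). For the interaction it is √2 × 0.097 = 0.137 (0.139 simulated). With the randomization value it is 0.137 × √(1 − 0.5²) = 0.119 (0.120 simulated). The plan's 10% yardstick is 0.65 / 2.56 = 0.254 µM per SD. Power there is about 43% for the interaction, about 55% with the randomization value, and about 72% for an O₂-only regression. About 82% needs 0.35 µM per SD, which is 0.35 × 2.56 = 0.90 µM, or 14% of 6.5.

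**The case against.** **The regression is open, not closed.** Its sentence refers to exposure without naming O₂, under an aim that names both exposures, so a model with both arms and an interaction is not excluded. This stands. A reader might infer that no form of the planned regression could answer the question, and the documents do not support that. The defect is that the necessary term is not specified. Separate slopes by arm would also be a legitimate start, but no test of their difference is planned. Judging by which arm reaches significance would mislead: at r = 0.2 with no duration effect, the O₂ slope is significant and the RA slope is not in about 24–25% of trials.

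**The hypotheses are associational.** Both statements of the hypothesis, in Specific Aims and in Secondary Aim 1, speak of a relation between duration and marker level, and the ANOVA does test that. This also stands. However, the Specific Aims heading and the regression sentence speak of an effect of duration, and the stated use of the result is to guide O₂ administration. An association that may be labour alone cannot serve that use.

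**There is outside support for dose-response.** The background cites a randomized O₂-versus-RA trial in scheduled cesareans, where advancing labour is an unlikely explanation. That makes the hypothesis more plausible but does not repair this trial's test.

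**Other parts of the plan do not fill the gap.** Covariate adjustment under Primary Aim 1 belongs to the arm comparison and names no time variable. The room-air trend graph in Secondary Aim 2 is of urine, in induced patients only, and descriptive. The randomization sample removes differences already present then, not what follows.

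**The percentages are assumed.** True: at r = 0 the ANOVA behaves nominally. Only MDA was simulated, since no SD for 4-HNE is given.

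**Conclusion.** The point holds as an under-specification of a secondary analysis that is worth correcting. The inability of the stated O₂-only tests, or of a pooled model without an interaction, to separate the two explanations follows from O₂ running until delivery and needs no assumed figures. How often this would produce a false duration claim does depend on assumptions: about 5% with no labour trend, rising to about 62% at r = 0.3.

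Two further inferences should be resisted. The documents do not show that MDA or 4-HNE rises with labour in this population, so it cannot be said that a positive duration result would be wrong, only that it would be uninterpretable as planned. Nor does the point reach the randomized comparison of O₂ with RA, which does not depend on duration.

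**What to change.** In all randomized patients, regress post-delivery maternal MDA, and separately 4-HNE, on assigned arm, time from randomization to delivery on the log scale, arm-by-time, and the randomization value. Name the arm-by-time term as the test of whether O₂ duration matters beyond elapsed labour. Keep the five bands as description, shown for both arms, and compare the randomization-to-delivery interval between arms. As an optional sensitivity analysis, record the blood-draw time and adjust for the delay from delivery to draw.

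The operational cost is SAP wording and one model, plus the draw time if the sensitivity analysis is adopted. Two statistical costs should be stated:

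1. The interaction is less precise than an O₂-only slope, and at the plan's 10% yardstick its power is modest. Report the estimate with its confidence interval, and do not read a null interaction as absence of a duration effect.
2. Time to delivery is measured after randomization in an unblinded trial, so the test assumes that arm does not materially change it. In simulation the rejection rate stayed at 5–6% with medians of 60 versus 45 min by arm.

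The log scale matters: if the trend is in log time, a plain linear time term rejects in 8–10% of trials at r = 0.3.
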